4.4.2.3 Keyhole Limpet Hemocyanin

KLH is a high molecular weight respiratory metalloprotein found in the hemolymph of many mollusks and crustaceans. However, KLH does not have regulatory approval and is not marketed. Therefore, it may be considered an investigational medicinal product (IMP) in some regions. KLH has been used in global clinical trials as a challenge agent to evaluate patient's immune responses to neo-antigen (Mestecky et al. 2005; Miller et al. 2005; Spazierer et al. 2009). In this study, KLH will be used to test primary humoral response following B-cell depletion with OCR.

Group A patients will receive subcutaneously (SC) administered KLH (1 mg) at Day 85/Week 12, Day 112/Week 16, and Day 140/Week 20.

Group B patients will receive SC administered KLH (1 mg) at Day 1/Week 1, Day 28/Week 4, and Day 56/Week 8.

4.4.2.4 Conjugate Pneumococcal Vaccine

This study will assess antibody production when administered as 13-PCV booster vaccine after 23-PPV vaccine. The 13-PCV is indicated as active immunization for the prevention of pneumonia and invasive disease caused by 13 *Streptococcus pneumoniae* serotypes (1, 3, 4, 5, 6A, 6B, 7F, 9V, 14, 18C, 19A, 19F, and 23F). It has been chosen for this study to assess antibody production when administered as 13-PCV booster vaccine after 23-PPV vaccine (the response to serotype 6A will not be tested in the assay used in this study). Booster 13-PCV will be administered in the deltoid muscle as a single IM injection.

Group A1 patients will receive the 13-PCV at Week 20/Day 140. Refer to the label for dosing and administration guidance.

4.4.2.5 Seasonal Influenza Vaccine

The influenza vaccine is indicated for immunization against influenza caused by the influenza strains included in the vaccine. The inactivated (or recombinant) vaccine has

been chosen for this study to assess antibody production for a commonly used clinically relevant antigen.

Group A2 patients can receive the influenza vaccine at any time between Day 85/Week 12 and Day 140/Week 20.

Group B patients will receive the influenza vaccine as an IM injection in the deltoid muscle at any time between Day 1/Week 1 and Day 84/Week 12. If a patient needs to receive the influenza vaccine after Week 12, the optional OCR infusion must be delayed.

Group A1 patients can receive the influenza vaccine at any time at the discretion of the investigator.

Refer to the label for dosing and administration guidance.

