- Safety Follow-Up (SFU) Period: *Patients who discontinue treatment early for any reason and patients who complete the study treatment period will be followed up for 48 weeks after the last infusion of OCR. When patients begin an alternative treatment for MS (see Section 4.6.3.1 on prohibited therapies), or start treatment with commercial OCR, they will be discontinued from the SFU and from the study.*

A schedule of assessments is provided in [Appendix 1](#). Study Schemas are provided in [Figure 1](#) and [Figure 2](#).

Figure 1 Schema of Study Periods

OCR=ocrelizumab; OOE=Optional Ocrelizumab Extension Period; SFU=safety follow-up.

Figure 2 Study Schema

[figure not shown]

Figure 2 Study Schema (cont.)

KLH=keyhole limpet heamocyanin; *OCR*=*ocrelizumab*; PCV=pneumococcal conjugate vaccine; PPV=polysaccharide pneumococcal vaccine; TT=tetanus toxoid-containing vaccine; Wk=week

Influenza vaccine: Group B: The influenza vaccine can be given any time between Week 1 and 12. If a patient needs to receive the vaccine after Week 12, the *OCR* infusion can be delayed. For patients in Group A2 and Group B who, as per the Schedule of Assessment, are due to receive the influenza vaccine during their country-specific influenza vaccine blackout period, administration of the vaccine should be given prior to the start of this blackout period.

***Group A split:** Patients assigned to Group A2 will receive the influenza vaccine. Patients assigned to Group A1 will receive the 13-PCV booster.

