3.3.2.4 Influenza Vaccine

Group A (active) patients are to be split and patients assigned to Group A2 will receive the influenza vaccine after OCR administration (refer to Section 3.1 for details on the assignment on patients to Group A1 or A2). Patients can receive the influenza vaccine at any time between Weeks 12 and 20. Serum titers will be measured 4 weeks after the initial vaccine administration and will be compared with levels immediately prior to vaccine administration.

Group B patients can receive the influenza vaccine between Week 1 and 12. If necessary, Group B patients can receive the influenza vaccine after Week 12, in which case the OCR infusion visit must be delayed. Serum titers will be measured 4 weeks after vaccine administration and will be compared with levels immediately prior to vaccine administration.

Group A1 patients can receive the influenza vaccine at any time at the discretion of the investigator.

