4.1.3 Eligibility for the Optional Ocrelizumab Extension Period

Only patients who have completed the Immunization Study Period are potentially eligible for the Optional OCR Extension Period.

Prior to re-treatment with OCR, patients will be evaluated for the following conditions and laboratory abnormalities.

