4.3.2 Dosage, Administration, and Compliance

4.3.2.1 Ocrelizumab

The infusion solution must be administered using an infusion set with an in-line, sterile, non-pyrogenic, low-protein-binding filter (pore size of 0.2 to 0.22 µm). OCR may contain fine translucent and/or reflective particles associated with enhanced opalescence. Do not use the solution if it is discolored or if the solution contains discrete foreign particulate matter.

Mandatory premedication is required prior to any infusion with OCR (see Section 4.4.1).

During the Immunization Study Period:

- Patients in Group A will be administered OCR by IV infusion at a dose of 300 mg on Day 1/Week 1 (Dose 1 Infusion 1) and Day 15/Week 2 (Dose 1 Infusion 2).
- Patients in Group B will not receive any OCR.

During the OOE, for patients who meet the criteria for optional OCR treatment (refer to Section 4.1.3 and Section 4.1.4):

- Patients from Groups A1 and A2 will be administered OCR by IV infusion at a dose of 600 mg on Day 169/Week 24 (Dose 2) and subsequent 600 mg single infusions with an interval of 24 weeks (minimum interval of 22 weeks).
- Patients from Group B will be administered OCR by IV infusion at a dose of 300 mg on Day 84/Week 12 (Dose 1 Infusion 1) and Day 98/Week 14 (Dose 1 Infusion 2) and at a dose of 600 mg on Day 252/Week 36 (Dose 2) and subsequent 600 mg single infusions with an interval of 24 weeks (minimum interval of 22 weeks).

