4.6.4 Immunizations

Physicians are advised to review the immunization status of patients who are considered for treatment with OCR and follow local/national guidance for adult vaccination against infectious disease. Known dates of immunizations will be recorded on specific eCRF pages, i.e., 'Vaccination History'. Immunizations (excluding tetanus-containing vaccines, 23-PPV, influenza, and 13-PCV) should be completed at least 6 weeks prior to first administration of OCR.

Patients who require de novo hepatitis B vaccination (three separate doses of vaccine) should also have completed the course at least 6 weeks prior to the first infusion of study drug.

The safety of immunization with live or live-attenuated vaccines following OCR therapy has not been studied. Immunization with any live or live-attenuated vaccine (i.e., measles, mumps, rubella, oral polio vaccine, *bacille Calmette-Guérin*, typhoid, yellow fever, vaccinia, cold adapted live influenza strain vaccine, or any other vaccines not yet licensed but belonging to this category) is not recommended within 6 weeks of first dosing (see Section 4.1.2), during OCR treatment, and for as long as the patient is B-cell depleted.

Patients who are eligible for a yearly influenza vaccine or who require immunizations or boosters for other diseases can receive immunization with killed/toxoid vaccines consistent with normal clinical practice.

For details regarding vaccinations during OCR treatment, please refer to the current version of the Ocrelizumab Investigator's Brochure.

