5/Statistical Analysis Plan BN29739

Clinical Study Report: ocrelizumab - F. Hoffmann-La Roche Ltd
Protocol BN29739 Report Number 1079337

1. **BACKGROUND**

This Phase IIIb, multicenter, randomized, open-label study is designed to evaluate immune response to vaccines in patients with relapsing forms of multiple sclerosis (MS) after administration of a dose of ocrelizumab.

The clinical cutoff date (CCOD) will be the earliest date on which all randomized patients will have completed the Week 24 visit for Group A, completed the Week 12 visit for Group B, or prematurely discontinued during the Immunization Study Period (ISP) if they have discontinued before the Week 24 visit for Group A or before the Week 12 visit for Group B.

The scope of this statistical analysis plan includes the following:

- The primary analysis of immunology and safety endpoints evaluated in the ISP
- Analysis of all data available at the CCOD from the following periods:
 - The Optional Ocrelizumab Extension (OOE) after completing the ISP
 - The Safety Follow-Up (SFU) Period after the ISP for patients who did not enter the OOE
 - The SFU Period after completing the OOE

2. **STUDY DESIGN**

This Phase IIIb, multicenter, randomized, open-label study is designed to evaluate immune response to vaccines after administration of a dose of ocrelizumab.

The study consists of the following periods: Screening, an ISP, an OOE, SFU, and a Continued B-cell Monitoring Period.

Following screening, approximately 100 adult patients will be randomized into Groups A and B (2:1 active:control) to compare responses to immunization. Patients in Group B are to receive immunization with tetanus toxoid (TT)-containing adsorbed vaccine, 23-valent pneumococcal polysaccharide vaccine (23-PPV), influenza vaccine, and repeated administration with keyhole limpet hemocyanin (KLH). Group B patients will not receive ocrelizumab, but will remain treatment-naïve or continue with interferon beta (IFN- β) treatment until optional ocrelizumab treatment at the end of the ISP.

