2.4 ANALYSIS TIMING

The primary analysis of immunology and safety endpoints evaluated in the ISP and the analysis of available OOE data will be performed at the CCOD, which is defined as the date when all randomized patients have completed the Week 24 visit for Group A or the Week 12 visit for Group B, or the date on when all randomized patients have prematurely discontinued the ISP if they have discontinued before the Week 24 visit for Group A or before the Week 12 visit for Group B.

Regular interim safety analyses may be performed, approximately every 6 months, to allow pooled safety analyses of MS patients treated with ocrelizumab. These analyses are not described in this document.

Interim pharmacokinetic (PK) analyses may also be performed during the study. These PK analyses are not described here but in a separate document.

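### Group B influenza titers due after Day 84 can follow the first ocrelizumab infusion, and the SAP's general rules would still count them in the untreated comparator (minor)

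*Protocol*

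**What the plan says.** **Protocol**

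- *Vaccination window.* Section 4.4.2.5 and Appendix 1, Table B, note 26 allow influenza vaccination in Group B from Day 1 through Day 84.
- *Delay rule.* It is worded only for later vaccination: "If a patient needs to receive the influenza vaccine after Week 12, the optional OCR infusion must be delayed". Section 3.3.2.4 agrees ("in which case the OCR infusion visit must be delayed"), as do the Synopsis and note 26. The Figure 2 note in section 3.1 has only "infusion can be delayed". None of these gives a length of delay or ties it to the titer.
- *Titer.* It is due four weeks after vaccination (3.3.2.4; note 26).
- *OCR start.* Optional OCR in Group B is scheduled for Day 84 and Day 98 (4.3.2.1).
- *Entry to the extension.* "Only patients who have completed the Immunization Study Period are potentially eligible for the Optional OCR Extension Period" (4.1.3). Section 3.1 and Table B, note 2 end Group B's Immunization Study Period (ISP) on Day 84.
- *Vaccination before OCR.* The six-week rule in 4.6.4 exempts influenza vaccine: "Immunizations (excluding tetanus-containing vaccines, 23-PPV, influenza, and 13-PCV) should be completed at least 6 weeks prior to first administration of OCR".
- *Comparator.* Objective 4 (section 2.2) compares Group A2 with Group B as patients who have not received OCR.

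**SAP**

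- The scope in section 1 is "The primary analysis of immunology and safety endpoints evaluated in the ISP", together with data available from later periods. Section 2.4 adds that "the analysis of available OOE data will be performed at the CCOD".
- Section 4.1.2 analyzes immunization outcomes in randomized patients who complete the ISP, by randomized group. Section 4.4 drops only missing titers and plans no hypothesis tests.
- Section 4.4.2.4 compares A2 with B at four weeks and sets no condition on OCR start. Its one caution is that assignment to A2 was not random.

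**The concern.** The vaccination window closes on the day OCR opens, and the outcome is read 28 days after vaccination. A patient can therefore keep to every stated rule and still give the four-week sample after starting OCR. The SAP's general rules then leave that sample in the control group.

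What is at stake is the A2-versus-B influenza comparison. If OCR given shortly after vaccination lowers the titer at all, Group B looks more like A2 and each contrast (seroprotection, two-fold and four-fold rise, seroconversion, geometric mean titers) moves toward no difference. A reader of the tables could not tell how many such titers were included.

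**Working it through.** The plan gives no figure on this point. Its half-width of 0.201 is for the tetanus contrast and is not used here.

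**1. Day count.** Let v be the vaccination day (1 to 84), with the titer on day v + 28. OCR is on Days 84 and 98. Table B, note 27 has blood drawn before premedication on infusion days, so a Day 84 sample precedes OCR and a Day 98 sample precedes infusion 2.

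- After infusion 1: v + 28 > 84, so v ≥ 57.
- After both infusions: v + 28 > 98, so v ≥ 71.

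| Vaccinated on Day | Titer on Day | OCR before the titer | Vaccine to infusion 1 |
|---|---|---|---|
| 1–56 | 29–84 | none | 83 to 28 days |
| 57–70 | 85–98 | infusion 1, 1–14 days earlier | 27 to 14 days |
| 71–84 | 99–112 | both; infusion 1 was 15–28 days earlier | 13 to 0 days |

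The affected days are 28 of 84 (33%). The ±4-day window on the Day 84 visit moves the first affected day to 53 (OCR on Day 80) or 61 (OCR on Day 88).

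**2. Is the gap confined to this cell?** On nominal days, yes. A2's last influenza titer is on Day 140 + 28 = 168, before Dose 2 on Day 169. Group B's eight-week tetanus titer is on Day 56. Its last pneumococcal and KLH samples are on Day 84, before infusion.

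**3. Does another rule prevent it?** The delay rule starts only after Week 12. The six-week rule exempts influenza vaccine. The extension entry rule requires a completed ISP, but that period is written as ending on a fixed day, not at the influenza titer.

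**4. Size of any attenuation.** Let D be the true A2-minus-B difference, f the share of analyzed Group B titers drawn after OCR, and r the fraction of the full A2 effect present in those titers. The observed difference is D × (1 − f × r). Neither f nor r is in the documents. As illustration only, with vaccination days uniform over Day 1–84:

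- Everyone starts OCR on time: f = 28/84 = 0.333. Attenuation is 0% at r = 0, 8.3% at r = 0.25 and 33.3% at r = 1.
- A quarter start OCR and all late titers are obtained: f = 0.333 × 0.25 = 0.083. Attenuation is 2.1% at r = 0.25.

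**5. Precision if post-OCR titers are set aside.** Half-width = 1.96 × √(0.25/33 + 0.25/nB), assuming 33 in A2, p = 0.5 and about 33 in Group B (100/3).

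- nB = 33: 0.241.
- nB = 33 − 33 × 28/84 = 22: 0.270.

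Patients who decline OCR complete the study at Week 12 without follow-up (Protocol 3.1), so their late titers may be missing. At 25% uptake on uniform days that is 33 × 28/84 × 0.75 = 8.25 missing. It leaves 24.75, with a half-width of 0.261 before anything is set aside.

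**The case against.** The best defense is that the protocol already means the titer to come first. Section 3.1 describes the ISP as the time when Group B is immunized and has its post-immunization assessments. Table B, note 2 wants ISP assessments done on all patients, and 4.1.3 admits only ISP completers to OCR. The delay rule points the same way. This stands as evidence of intent. It does not settle the matter, because the ISP end is a fixed Day 84 and nothing requires the influenza titer before the first infusion. The broken Table B influenza row cannot decide it either.

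A reader might infer that the SAP is silent, or that its ISP scope wording drops these titers. Neither is supported. The general rules give a default, which is to keep every non-missing titer from an ISP completer in the randomized group. The scope sentence is not an exclusion rule, and the SAP also covers available extension data. The trouble is that this default does not match objective 4.

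It is also fair to say that vaccination dates need not be uniform, since the protocol directs vaccination before any blackout period, and that an effect on the titer may be small. These patients are vaccinated 0 to 27 days before OCR rather than 12 or more weeks after it, and the protocol notes that plasma cells lack CD20. An effect is not excluded: Protocol 1.1.4 reports CD19+ depletion by Day 15.

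Finally, SAP 4.4.5 permits a repeat analysis for other issues. It is optional, and vaccination inside the permitted window is not a deviation.

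**Conclusion.** The point holds as a minor one. Following both documents as written can place OCR-exposed titers in a comparator that objective 4 describes as not having had OCR. Any bias would be toward no difference. The number of patients and the effect size are undocumented and may be zero; the illustrations above rest on assumed vaccination dates, uptake and r.

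Three stronger conclusions might be drawn, and the documents support none of them:

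- *A third of Group B is contaminated.* The 33% is a share of permitted days, not of patients.
- *The reported influenza result is unsafe.* Protocol 5.1.1.6 already reports a decreased response with OCR. A bias toward no difference would not create that finding; only its size could be affected.
- *The trial's main conclusion is at risk.* The primary tetanus endpoint is unaffected, and the influenza contrasts are secondary and descriptive.

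**What to change.** In SAP 4.4.2.4:

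- Flag and count Group B influenza titers drawn after that patient's first OCR infusion, treating same-day pre-infusion samples as before OCR.
- Report how many late Group B titers are missing.
- Show the A2-versus-B contrasts on all titers and on pre-OCR Group B titers. State that the second version is free of OCR exposure but selects on vaccination date and elective OCR uptake in Group B only.
- If results are already known, as Protocol 1.1.4 and 5.1.1.6 indicate, label this a supplementary re-analysis.

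In the protocol, the Group B vaccination window, the Day 84 OCR start, the extension entry rule and the two delay wordings ("in which case the OCR infusion visit must be delayed" against "infusion can be delayed") must be reconciled. No schedule is proposed here.

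The cost is some SAP text and a second set of influenza tables; OCR administration dates are already logged (Protocol 4.4.3). The pre-OCR version has a smaller Group B and a somewhat wider interval, up to about 0.27 against 0.241 under the assumptions above, and the gap is narrower if decliners' late titers are already missing.

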4.4.3 Investigational Medicinal Product Accountability

The investigator is responsible for the control of drugs under investigation. Adequate records for the receipt and disposition of the study drug must be maintained.

Accountability will be assessed by maintaining adequate drug dispensing and return records.

Accurate records must be kept for each study drug provided by the Sponsor. These records must contain the following:

- Documentation of drug shipments received from the Sponsor (date received and quantity)
- Disposition of unused study drug not dispensed to patient.

A Drug Dispensing Log must be kept current and should contain the following information:

- The identification of the patient to whom the study drug was administered
- The date[s] and quantity of the study drug administered to the patient

All records and drug supplies must be available for inspection/accountability by the monitor at every monitoring visit.

4.4.3.1 Assessment of Compliance

Patient compliance will be assessed by maintaining adequate study drug dispensing records. The investigator is responsible for ensuring that dosing is administered in compliance with the protocol. Delegation of this task must be clearly documented and approved by the investigator.

The study pharmacist should keep all OCR vials to measure compliance.

4.4.4 Destruction of the Investigational Medicinal Product

Local or institutional regulations may require immediate destruction of used IMP for safety reasons. In these cases, it may be acceptable for investigational site staff to destroy dispensed IMP before a monitoring inspection provided that source document verification is performed on the remaining inventory and reconciled against the documentation of quantity shipped, dispensed, returned and destroyed. Written authorization must be obtained from the Sponsor at study start up before destruction. Written documentation of destruction must contain the following:

- Identity (batch numbers or medication numbers) of IMP destroyed
- Quantity of IMP destroyed
- Date of destruction
- Method of destruction
- Name and signature of responsible person who destroyed the IMP

Wherever possible, preferably drug should be destroyed locally on site according to their local policies and procedures once drug accountability has been completed by the monitor.

4.5 POST-TRIAL ACCESS TO OCRELIZUMAB

The Sponsor will offer continued access to OCR free of charge to eligible patients in accordance with the Roche Global Policy on Continued Access to Investigational Medicinal Product, as outlined below.

A patient will be eligible to receive OCR after completing the study if all of the following conditions are met:

- *The patient has a life-threatening or severe medical condition and requires continued OCR treatment for his or her well-being*
- *There are no appropriate alternative treatments available to the patient*
- *The patient and his or her doctor comply with and satisfy any legal or regulatory requirements that apply to them*

A patient will not be eligible to receive OCR after completing the study if any of the following conditions are met:

- *OCR is commercially marketed in the patient's country and is reasonably accessible to the patient (e.g., is covered by the patient's insurance or wouldn't otherwise create a financial hardship for the patient)*
- *The Sponsor has discontinued development of OCR or data suggest that OCR is not effective for MS*
- *The Sponsor has reasonable safety concerns regarding OCR as treatment for MS*
- *Provision of the OCR is not permitted under the laws and regulations of the patient's country*

The Roche Global Policy on Continued Access to Investigational Medicinal Product is available at the following website:

http://www.roche.com/policy_continued_access_to_investigational_medicines.pdf

